## 9 Assessment of Safety

### 9.1 Specific Safety Parameters

#### 9.1.1 Definition of Adverse Events (AE)

An AE is any untoward medical occurrence in a subject whether or not related to the investigational medical device.

Specifically, an adverse event (AE) is **any** undesirable experience (sign, symptom, illness, abnormal laboratory value, or other medical event) occurring to a subject during the course of the study, whether or not it is related to the device or procedure. Physical findings (including vital signs) observed at follow-up, or pre-existing physical findings that worsen compared to baseline are considered adverse events.

Any medical condition that is present at the time that the participant is screened will be considered as baseline and not reported as an AE. Such conditions should be added to background medical history, if not previously reported. However, if the study participant's condition deteriorates at any time during the study, it will be recorded as an AE.

AF recurrence by itself is considered a recurrence of disease (pre-existing condition), and, therefore, **does not meet the definition of an AE**. Recurrence of pre-existing AFL/ atrial tachycardia (AT) is also considered recurrence of disease, and does not meet the definition of an AE.

The following clinical events **will not be considered an adverse event for this clinical study**:

- Minor pericarditis attributable to the ablation procedure defined as pleuritic chest discomfort with or without pericardial rub and ECG changes.
- AF/AFL/AT recurrence requiring pharmacological or synchronized electrical cardioversion during the hospitalization for the index ablation procedure, or throughout the duration of the study. However, new onset of left atrial flutter occurring post-ablation is an AE. Re-ablation for AF or pre-existing AFL/AT itself is not an AE, however any procedural complication is considered an AE and shall be reported within the applicable timelines.

#### 9.1.2 Definition of Serious Adverse Event (SAE)

A serious adverse event (SAE) is any event that meets one or more of the following criteria:

- Leads to a death
- Leads to a serious deterioration in the health of a subject that resulted in:
  - A life-threatening illness or injury

- An injury or permanent impairment of a body structure or a body function
- In-patient hospitalization or prolongation of an existing hospitalization\*
- Medical or surgical intervention to prevent life-threatening illness or injury or permanent impairment to body structure or a body function
- Leads to fetal distress, fetal death or a congenital abnormality or birth defect.

Planned hospitalization for a condition present prior to the participant’s enrollment in the study will not meet the definition of an SAE. An AE would meet the criterion of “hospitalization” if the event necessitated an admission to a health care facility (e.g., an overnight stay). Emergency room visits that do not result in admission to the hospital should be evaluated for one of the other serious outcomes.

### 9.1.3 Primary Adverse Event

A Primary AEs is an event listed in Table 9.1.3A which occurs within the first week (7 days) following an ablation procedure.

**Table 9.1.3-A: Primary Adverse Events**

Primary Adverse Event	Description / Criteria
Death*	Subject death directly related to the device or procedure and occurs at any time during or after the procedure.
Atrio-Esophageal Fistula*	Defined as a connection between the atrium and the lumen of the esophagus. Evidence supporting this diagnosis includes documentation of esophagus erosion combined with evidence of a fistulous connection to the atrium such as air emboli, an embolic event, or direct observation at the time of surgical repair. A CT or MRI scan is the most common method of documentation of an atrio-esophageal fistula.
Myocardial Infarction	Presence of any one of the following criteria: 
 
- Detection of ECG changes indicative of new ischemia (new ST-T changes or new left bundle branch block [LBBB]) that persist for more than 1 hour
 
- Development of new pathological Q waves on ECG
 
- Imaging evidence of new loss of viable myocardium or new regional wall motion abnormality
 

Cardiac Tamponade**/Perforation	The development of a significant pericardial effusion during or within 30 days of undergoing the index AF ablation procedure. A significant pericardial effusion is one that results in hemodynamic compromise, requires elective or urgent pericardiocentesis, or results in a 1cm or more pericardial effusion as documented by echocardiography  Cardiac tamponade/perforation should also be classified as: Early – diagnosed prior to discharge Late – following initial discharge from the hospital

Primary Adverse Event	Description / Criteria
Thromboembolism	
Formation of a clot (thrombus) inside a blood vessel causing obstruction to blood flow. The thrombus can migrate (embolus) and obstruct distal vascular sites. Diagnostic tests to help detect thromboembolisms may include but are not limited to angiography (pulmonary or distal), ventilation-perfusion (V/Q) scans, venography, Doppler ultrasonography, spiral CT, and echocardiography.

Stroke/Cerebrovascular Accident (CVA)	
Diagnosis:
 
 
-Rapid onset of a focal or global neurological deficit with at least one of the following: change in level of consciousness, hemiplegia, hemiparesis, numbness or sensory loss affecting one side of the body, dysphasia or aphasia, hemianopia, amaurosis fugax, or other neurological signs or symptoms consistent with stroke.
 
-Duration of a focal or global neurological deficit <math>\geq 24</math> h; or <math>< 24</math> h, if therapeutic intervention(s) were performed (e.g. thrombolytic therapy or intracranial angioplasty); OR available neuroimaging documents a new hemorrhage or infarct; or the neurological deficit results in death.
 
-No other readily identifiable non-stroke cause for the clinical presentation (e.g., brain tumor, trauma, infection, hypoglycemia, peripheral lesion, pharmacological influences).†
 
-Confirmation of the diagnosis by at least one of the following: Neurology or neurosurgical specialist; Neuroimaging procedure (MR or CT scan or cerebral angiography); Lumbar puncture (i.e., spinal fluid analysis diagnostic of intracranial hemorrhage)
 
 
Definition:
 
Stroke: (diagnosis as above, preferably with positive neuroimaging study)
 
 
Minor—Modified Rankin score <math>< 2</math> at 30 and 90 days††
 
Major—Modified Rankin score <math>\geq 2</math> at 30 and 90 days
 

Transient Ischemic Attack	
New focal neurological deficit with rapid symptom resolution (usually 1 to 2 h), always within 24h; neuroimaging without tissue injury.

Phrenic Nerve Paralysis	
Absent phrenic nerve function as assessed by a sniff test, associated with symptoms of dyspnea and orthopnea (diagnosed by chest x-ray). A phrenic nerve paralysis is considered to be permanent when it is documented to be present 12 months or longer following ablation. Under this protocol, diaphragmatic paralysis/phrenic nerve palsy will be considered a Primary AE if specified symptoms have not improved at the 3- month visit

Primary Adverse Event	Description / Criteria
Pulmonary Vein Stenosis*	A reduction of the diameter of a PV. Severe PV stenosis ( $\geq 70\%$ reduction in the diameter of the PV) will be considered a primary adverse event and major complication of AF ablation.
Major Vascular Access Complication /Bleeding	Major Bleeding: Requires and/or treated with transfusion or results in a 20% or greater fall in hematocrit.  Major Vascular Access Complication: Defined as a hematoma, an AV fistula or a pseudoaneurysm which requires intervention such as surgical repair or transfusion, prolongs the hospital stay, or requires hospital admission.

\* Device or procedure related death, atrio-esophageal fistula and pulmonary vein stenosis that occur greater than one week (7 days) and ( $\leq$ ) less or equal to 90 days post-procedure shall be deemed Primary AE.

\*\* Hemodynamic compromise or instability is defined as Systolic blood pressure < 80 mmHg

† Patients with non-focal global encephalopathy will not be reported as a stroke without unequivocal evidence based upon neuroimaging studies.

†† mRS assessments should be made by qualified individuals according to a certification process. If there is discordance between the 30 and 90 day mRS, a final determination of major versus minor stroke will be adjudicated by an independent physician/committee.

#### 9.1.4 Adverse Device Effect / Serious Adverse Device Effect

An adverse device effect is an adverse event related to the use of the investigational medical device.

NOTE 1- This includes any adverse event resulting from insufficiencies or inadequacies in the instructions for use, the deployment, the implantation, the installation, the operation, or any malfunction of the investigational medical device.

NOTE 2- This includes any event that is a result of a use error or intentional abnormal use of the investigational medical device.

A Serious Adverse Device Effects (SADE) is an adverse device effect that has resulted in any of the consequences characteristic of an SAE.

#### 9.1.5 Unanticipated (Serious) Adverse Device Effect

An unanticipated adverse device effect (UADE) or unanticipated serious adverse device effect (USADE) is any serious adverse effect on health, safety, any life-threatening problem, or death caused by, or associated with a device, if that effect, problem, or death was not previously identified in nature, severity, or degree of incidence in the investigational plan or risk analysis

report, or any other unanticipated serious problem associated with a device that relates to rights, safety, or welfare of subjects. Refer to Table 9.2.4A for a comprehensive list of foreseeable and anticipated adverse events.

### 9.1.6 Study Device Deficiency, Failure or Malfunction

A device has failed if it does not perform according to the IFU or fails to meet the expectations of the device and/or investigator (i.e., related to appearance of the device, performance, durability, safety, effectiveness, quality, reliability, labeling, etc.). If a device failure is detected or suspected, it should be documented on the appropriate eCRF and device failure and AE must be reported per section 9.4.1 AE documentation and reporting requirements.

## 9.2 Classification of an Adverse Event

### 9.2.1 Severity of Event

The intensity or severity of each AE must be assessed according to the following classifications:

**Table 9.2.1-A: Intensity or Severity Definitions**

Mild	Awareness of signs, symptoms, or events that are otherwise easily tolerated that may result in minimal transient impairment of a body function or damage to a body structure, but do not require intervention other than monitoring.
Moderate	Any event that results in moderate transient impairment of a body function or damage to a body structure that causes interference with usual activities, or that warrants possible intervention, such as the administration of medication, to prevent permanent impairment of a body function or damage to a body structure.
Severe	Any event that is incapacitating (an inability to do usual activities) or is life-threatening and results in permanent impairment of a body function or damage to a body structure, or requires intervention, such as major surgery, to prevent permanent impairment of a body function or damage to a body structure.

### 9.2.2 Relationship to Study Device

For all collected AEs, the clinician who examines and evaluates the participant will determine the AE's causality based on temporal relationship and his/her clinical judgment. The degree of certainty about causality will be graded using the categories below as described per MEDDEV 2.7/3 Rev3.

**Table 9.2.2-A: Adverse Event Causality Classifications**

Caused By	Relation	Definition of Relation
Device	Definitely (Causal Relationship)	The event is associated with the investigational device beyond reasonable doubt
	Probable	The relationship with the use of the investigational device seems relevant and/or the event cannot be reasonably explained by another cause, but additional information may be obtained
	Possibly	The relationship with the use of the investigational device is weak but cannot be ruled out completely
	Unlikely	The relationship with the use of the investigational device seems not relevant and/or the event can be reasonably explained by another cause, but additional information may be obtained
	Not related	Relationship to the investigational device can be excluded
Study Procedure	Definitely (Causal Relationship)	The event is associated with the study procedure beyond reasonable doubt
	Probable	The relationship with the study procedure seems relevant and/or the event cannot be reasonably explained by another cause, but additional information may be obtained
	Possibly	The relationship with the study procedure is weak but cannot be ruled out completely
	Unlikely	The relationship to the study procedure seems not relevant and/or the event can be reasonably explained by another cause, but additional information may be obtained
	Not related	Relationship to the procedure can be excluded

### 9.2.3 Outcome

The outcome of each AE must be assessed according to the following classifications:

**Table 9.2.3-A: Adverse Event Outcome Classifications**

Classification	Definition	
Resolved without sequelae	Subject fully recovered with no observable residual effects	
Resolved with sequelae	Subject recovered with observable residual effects	
Ongoing	Improved	Subject's condition improved, but residual effects remain
	Unchanged	AE is ongoing without changes in the overall condition
	Worsened	Subject's overall condition worsened
Death	Subject died as a result of the AE (whether or not the AE is related to the device or procedure)	

### 9.2.4 Expectedness

An anticipated Adverse Event is an effect which by nature, incidence, severity or outcome has been identified as a possible complication associated with the investigational medical device and/or intervention procedure.

Potential adverse events that are reasonably anticipated to occur during the cardiac electrophysiology procedure are listed in Table 9.2.4A. These events should be reported via EDC as anticipated AEs. Anticipated adverse events are to be reported to the sponsor via EDC as indicated in section 9.4.

**Table 9.2.4-A: provides a comprehensive list of anticipated AEs.**

Anticipated Adverse Events	
Acute Respiratory Distress Syndrome (ARDS)	Air embolism
Allergic reaction	Allergic reaction to Anesthesia (e.g., hair loss)
Anaphylactic shock	Anemia
Anesthesia reaction	Apnea - sedation induced
Arrhythmia: bradycardia	Arrhythmia: pro-arrhythmias
Arrhythmia: tachycardia	(Aspiration) pneumonia
Asthmatic attack	
Atelectasis	Atrial fibrillation*
Atrio-Esophageal fistula	Atypical left atrial flutter
AV fistula	Bleeding complications
Bleeding requiring transfusion	Cardiac arrest
Cardiac perforation	Cardiac thrombo-embolism
Cerebro-vascular accident (CVA) / stroke	Chest pain/discomfort
Complete heart block, temporary or permanent	Conduction block: ongoing / resolved
Congestive Heart Failure	Coronary artery dissection
Coronary artery occlusion	Coronary artery spasm
Coronary artery Thrombosis	Damage to the vascular system
Death	Deep venous thrombosis
Diaphragmatic paralysis	Dislodgement of permanent pacing leads
Disseminated Intravascular Coagulation	Dyspnoea
Endocarditis	Epistaxis
Exacerbation of pre-existing arrhythmia*	Expressive aphasia
Fainting	Fatigue
Gastric reflux	Gastrointestinal diverticulosis
Gastro-intestinal NOS	Heart Failure
Hematoma (local) / ecchymosis	Hemorrhage
Hemothorax	High / increased creatine phosphokinase (CPK)
Hypotension	Hypoxia

Increase in frequency or duration of episodes of typical atrial flutter	Increased phosphokinase level
Infection, localized	Infection, systemic
Injury to skin, muscle, connective tissue due to body position, electrical cardioversion, etc.	Laceration
Leakage of air or blood into the lungs or other organs due to perforation	Liver toxicity
Local hematoma/ecchymosis	Mobile strands in Inferior Vena Cava
Myocardial Infarction	Nausea
Neurological disorders (headache)	Neurological disorders (poor coordination)
Neurological disorders (tremor)	Obstruction to the vascular system
Palpitations	Perforation to the vascular system
Pericardial effusion without tamponade	Pericardial effusion resulting in tamponade
Peripheral embolus	Pericarditis
Peripheral thromboembolism	Peripheral nerve injury
Phrenic nerve damage	Phlebitis
Pneumothorax	Pleural effusion
Pulmonary edema	Pseudoaneurysm
Pulmonary hypertension	Pulmonary embolism
Pulmonary vein dissection	Pulmonary toxicity, like acute pulmonary syndrome
Pulmonary vein thrombus	Pulmonary vein Stenosis
Renal failure	Pump failure
Respiratory failure	Respiratory depression
Rhabdomyolysis, including produced by body position or propofol	Retroperitoneal hematoma
Seizure	Sedation induced CO 2 retention with lethargy and cholecystitis
Skin burns (due to cardioversion, tape, etc)	Sepsis
Skin injury / muscle or connective tissue injury due to body position, electrical cardioversion	Skin discoloration
Tamponade	Skin rash
Thrombocytopenia	Temperature elevation
Thrombosis	Thromboembolism
Transient extremity numbness	Thyroid disorders
Unintended complete or incomplete AV, Sinus node, or other heart block or damage	Transient ischemic attack (TIA)
Urinary tract injury or infection related to the urinary catheter	Urinary retention
Vasovagal reactions	Valvular damage/insufficiency
Volume overload	Vision change
X-ray radiation injury of skin, muscle and/or organ	Worsening obstructive, restrictive, or other form of pulmonary disease

\*Atrial Fibrillation and exacerbation of an existing arrhythmia are anticipated adverse events. However, they will not be captured as such under this protocol, as they are considered recurrence of disease.]

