## 2 Objectives and Purpose

### 2.1 Objective

The primary objective of this clinical investigation is to demonstrate the safety and acute effectiveness of the Multi-Electrode Radiofrequency Balloon Catheter in conjunction with the multi-electrode circular diagnostic catheter, in the isolation of the atrial pulmonary veins in treatment of subjects with paroxysmal atrial fibrillation. Specifically:

- To demonstrate the safety based on the proportion of early-onset (within 7 days of ablation procedure) primary adverse events.
- To demonstrate the acute effectiveness based on the proportion of acute procedural success defined as confirmation of entrance block in treated PVs after adenosine and/or isoproterenol challenge (with or without the use of a focal ablation catheter).

The major secondary objective of this study is to evaluate the incidence of (serious) adverse events during and after procedure up to 12 months following procedure. The need for the use of a focal catheter (touch-up) to get to PV isolation will also be evaluated.

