6.2.2 Secondary Effectiveness Endpoints

- Percentage (%) of pulmonary vein isolation (PVI) touch-up by focal catheter among all targeted veins and by subject.
- Percentage (%) of subjects with use of focal catheter ablation for non-PV triggers
- 6-Month Documented Symptomatic AF Recurrence: Percentage (%) of subjects with freedom from documented, symptomatic atrial fibrillation (AF), atrial tachycardia (AT), or atypical (left side) atrial flutter (AFL) episodes (episodes >30 seconds on arrhythmia monitoring device from Day 91 to 180)
- 6-Month Documented AF Recurrence: Percentage (%) of subjects with freedom from documented, atrial fibrillation (AF), atrial tachycardia (AT), or atypical (left side) atrial

flutter (AFL) episodes (episodes >30 seconds on arrhythmia monitoring device from Day 91 to 180)

- 12-Month Documented Symptomatic AF Recurrence: Percentage (%) of subjects with freedom from documented, symptomatic atrial fibrillation (AF), atrial tachycardia (AT), or atypical (left side) atrial flutter (AFL) episodes (episodes >30 seconds on arrhythmia monitoring device from Day 91 to 365)
- 12-Month Documented AF Recurrence: Percentage (%) of subjects with freedom from documented, atrial fibrillation (AF), atrial tachycardia (AT), or atypical (left side) atrial flutter (AFL) episodes (episodes >30 seconds on arrhythmia monitoring device from Day 91 to 365)

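### The footnote to Table 9.2.4-A exempts worsening of any existing arrhythmia from AE capture, which is wider than section 9.1.1 and conflicts with the typical-flutter row, so the descriptive AE, SAE and SADE incidences may be inconsistent or understated

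*Protocol*

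**What the plan says.** Protocol 9.1.1 sets the general rule. A condition present at screening is baseline, but "if the study participant's condition deteriorates at any time during the study, it will be recorded as an AE". It adds that "pre-existing physical findings that worsen compared to baseline are considered adverse events". Its arrhythmia exemptions follow: AF recurrence on its own, recurrence of pre-existing flutter (AFL) or atrial tachycardia (AT), recurrence of these that needs cardioversion, and re-ablation itself. New left atrial flutter after ablation remains an AE.

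Section 9.2.4 tells sites to report the events in Table 9.2.4-A as anticipated AEs. Two rows carry an asterisk: atrial fibrillation, and exacerbation of a pre-existing arrhythmia. The footnote says of AF and the second row that "exacerbation of an existing arrhythmia are anticipated adverse events. However, they will not be captured as such under this protocol", and gives the reason "as they are considered recurrence of disease". Another row, "Increase in frequency or duration of episodes of typical atrial flutter", has no asterisk. Neither do the bradycardia, tachycardia and pro-arrhythmia rows.

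Protocol 2.1 states: "The major secondary objective of this study is to evaluate the incidence of (serious) adverse events during and after procedure". SAP 6.2.1 lists SADEs, SAEs by time window and non-serious AEs as secondary safety endpoints, and SAP 11.5.1 summarizes them descriptively. The SAP has no rule of its own on which arrhythmia events count.

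**The concern.** Recurrence and exacerbation are different things. Return of the treated arrhythmia is a failure of effectiveness, and there is good reason to keep it out of the AE record. An arrhythmia that becomes worse after ablation may be a harm of the procedure or device. The footnote treats the second as the first, and it covers any existing arrhythmia, not only those under treatment.

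At stake is whether the (S)AE incidences of a single-arm study intended to support CE marking were collected under one rule. If sites read different passages, the pooled rates depend in part on which passage each site followed.

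**Working it through.** No arithmetic applies: the documents state no expected rate of arrhythmia exacerbation. The check compares the passages event by event.

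| Event after ablation | Section 9.1.1 | Table 9.2.4-A and footnote | Result |
|---|---|---|---|
| Plain recurrence of AF or pre-existing AFL/AT, cardioverted or not | Not an AE | AF row starred | No conflict: not an AE |
| New left atrial flutter | AE | Atypical left flutter row unstarred | Agree: AE |
| Pre-existing AF/AFL/AT worse than plain recurrence | Deterioration rule makes it an AE; the exemption speaks only of recurrence | Starred exacerbation row: not captured | Conflict |
| Pre-existing typical flutter, more frequent or longer episodes | As above | One row reportable, the starred row not captured | Conflict with 9.1.1 and within the table |
| Worsening of another existing arrhythmia | Deterioration rule makes it an AE; no exemption applies | Starred row not captured; bradycardia, tachycardia or pro-arrhythmia row may apply | Depends on the row the site picks |

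The first two rows show that the footnote and 9.1.1 agree on plain recurrence and new left flutter. What the footnote adds is in the last three rows.

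The typical-flutter case can arise in this study. The protocol allows ablation in the cavotricuspid isthmus (CTI) region and, under section 8.2.2.3, gives a rule for confirming block when a CTI flutter line is placed.

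Consequences for the counts:

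1. **AE.** An event handled under the footnote is not recorded as an AE.
2. **SADE.** Section 9.1.4 defines an adverse device effect as an adverse event related to the device. An event that is not an AE cannot become a SADE, however serious or device-related it is.
3. **SAE.** Section 9.1.2 speaks of any event meeting a seriousness criterion and has no arrhythmia exemption. The footnote has no exception for serious events. The SAE status of a serious exacerbation is therefore unresolved.
4. **Primary safety.** None of the ten primary adverse events in protocol 3.2.1 and SAP 6.1.1 is an arrhythmia. The 15% goal, the exact test, the interim rules and the maximum of 230 are untouched.

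Other records hold part of the information. Recurrence of AF, AT or atypical flutter and repeat ablation are collected at months 1, 3, 6 and 12. Transtelephonic monitoring starts at month 1. Cardiovascular hospitalization is a separate endpoint. The freedom-from-arrhythmia endpoints begin later ("episodes >30 seconds on arrhythmia monitoring device from Day 91 to 180" for the first period) and, for flutter, count only the atypical left-sided form. Worsening typical flutter is the least protected event if a site follows the footnote.

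**The case against.** The strongest reply is that this is a wording conflict with limited effect. Section 9.1.1 already takes most early atrial arrhythmia out of AE capture, including cardioverted recurrence throughout the study, and a narrower footnote would leave it out. The footnote says only that these events are not captured as AEs; recurrence visits, transtelephonic monitoring and the unscheduled-visit form still record some of them. Consequences such as palpitations, fainting, heart failure and stroke have unstarred rows of their own. The sentence on worsening physical findings is about findings such as vital signs, so the argument rests mainly on the deterioration sentence. That sentence is a general rule, followed directly by arrhythmia-specific exceptions. The affected outputs are descriptive, the sponsor reviews AE classification (9.4.1), and a committee reviews safety events (9.5).

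Most of this stands and limits the point. It does not remove the conflict: the exceptions in 9.1.1 stop at recurrence and the footnote does not. Sponsor and committee can review only what sites report.

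A reader might infer more than the documents support:

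- **That worsening arrhythmia as a whole disappears from the safety rates, or that typical-flutter, ventricular and bradycardic events are uncovered throughout follow-up.** The unstarred rows keep such events reportable. Conflicting text points to uneven capture, not certain loss.
- **That the footnote leaves days 0 to 90 without coverage.** Much of that gap comes from 9.1.1 and from the day-91 start of the freedom endpoints, and monitoring begins at month 1.
- **That an assumed percentage of affected subjects can be read as the bias in each rate.** The documents offer no such percentage. An event is either serious or non-serious, so one figure cannot apply to all the incidences. A subject-level rate falls only if that subject has no other qualifying event.

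**Conclusion.** The point holds as an internal contradiction in an event-capture rule. The footnote is wider than 9.1.1 and disagrees with the typical-flutter row when the flutter pre-exists. A worsened arrhythmia, including a serious or device-related one, can be captured at one site and not at another. The secondary AE, SAE and SADE incidences may therefore be inconsistent or too low, by an amount that cannot be estimated from the documents. No primary conclusion and no sample-size figure changes.

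This rests on two assumptions: that the asterisks stand in the table as they appear in the text read here, and that no site instruction outside the protocol and SAP already settles which passage governs.

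**What to change.** Reconcile 9.1.1, the footnote and the two table rows:

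- Limit the footnote to the recurrence exclusions already in 9.1.1, for AF and pre-existing AFL/AT.
- Remove the asterisk from the row on exacerbation of a pre-existing arrhythmia, or restrict that row to the same recurrence exclusions.
- Align that row with the typical-flutter row, so that one event has one answer.
- State that an arrhythmia event that meets 9.1.2 or is device-related, and is not plain AF/AFL/AT recurrence, is recorded as an AE. It counts as an SAE if it meets 9.1.2, and as a SADE if it is also device-related.

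The new rule should turn on seriousness and device relation, not on a measured rise in frequency or duration from baseline. The schedule has no baseline rhythm monitoring: transtelephonic monitoring starts at month 1, Holter is at months 6 and 12, and baseline has only the AF history and an ECG if available.

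The cost is a change of wording in the protocol and in any matching eCRF guidance. Reported AE and SAE rates may become slightly less favourable. Plain AF/AFL/AT recurrence stays excluded, as now.
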